2. OBJECTIVES AND HYPOTHESES

2.1. Objectives

Primary Objectives

Part 1: To evaluate the efficacy and safety of imetelstat in transfusion dependent subjects with low or intermediate-1 risk MDS that is relapsed/refractory to ESA treatment.

Part 2: To compare the efficacy, in terms of RBC TI, of imetelstat to placebo in transfusion dependent subjects with low or intermediate-1 risk MDS that is relapsed/refractory to ESA treatment.

Extension Phase: To evaluate the long-term safety, OS, and disease progression, including progression to AML in transfusion dependent subjects with low or intermediate-1 risk MDS that is relapsed/refractory to ESA treatment receiving imetelstat.

Secondary Objectives (Part 1 and Part 2)

The secondary objectives of this study are:

- To assess the safety of imetelstat in subjects with MDS
- To assess the time to RBC TI and duration of RBC TI
- To assess the rate of hematologic improvement
- To assess the rates of CR, PR, and mCR
- To assess OS
- To assess progression free survival (PFS)
- To assess time to progression to AML
- To assess the rate and amount of supportive care, including transfusions and myeloid growth factors (Part 2 only)
- To evaluate the pharmacokinetics and immunogenicity of imetelstat in subjects with MDS
- To assess the effect of imetelstat treatment on patient-reported outcomes (PROs)
- To assess the effect of treatment on medical resource utilization (Part 2 only)
- To assess the effect of imetelstat on corrected QT (QTc) interval in subjects in the Ventricular Repolarization substudy (to be reported separately from Part 2)

Exploratory Objectives (Part 1 and Part 2)

The exploratory objectives of this study are:

- To evaluate pharmacodynamic biomarkers such as TA, TL and hTERT and to explore the association between baseline results and clinical response
- To evaluate change of cytogenetic abnormalities and explore the association between baseline cytogenetic status and clinical response

- To evaluate baseline mutational status and mutation changes during treatment for exploring the association with clinical response
- To explore the effects of imetelstat on immune profiles through immunophenotyping (Part 1 only)
- To evaluate the exposure-response relationship between pharmacokinetics and pharmacodynamic biomarkers, efficacy, and safety

2.2. Hypothesis

The primary hypothesis is that imetelstat will improve the rate of RBC TI as compared to placebo in transfusion dependent subjects with low or intermediate-1 risk MDS that is relapsed/refractory to ESA treatment.

3. STUDY DESIGN AND RATIONALE

3.1. Overview of Study Design

This is a Phase 2/3, multicenter study of imetelstat in transfusion-dependent subjects with low or intermediate-1 risk MDS that is relapsed/refractory to ESA treatment (see Inclusion Criterion 5, Section 4.1). The study will consist of 2 parts, and approximately 270 subjects may be enrolled (Figure 2). Part 1 was an open-label, single-arm design to assess the efficacy and safety of imetelstat, which enrolled 57 subjects. Part 2 is a double-blind, randomized, placebo-controlled design to compare the efficacy of imetelstat with placebo. In addition to the approximately 170 subjects to be enrolled in the main study in Part 2, approximately 45 subjects will be enrolled in a separate Ventricular Repolarization substudy. Subjects should be enrolled in the main study of Part 2 until enrollment is complete unless a subject is known to meet criteria that would make the subject ineligible for the main study (eg, del 5 q, prior HMA therapy). See Figure 2 for schematic overview of the study.

Part 1 was an open-label, single-arm design to assess the efficacy and safety of imetelstat. Fifty-seven subjects were enrolled in Part 1, including the expansion cohort, and were followed-up for safety, hematologic improvement, and reduction in transfusion requirement. The sponsor has reviewed and assessed all available data in Part 1, including blood counts, transfusion requirement, tolerability, pharmacokinetics, and pharmacodynamic biomarker data.

The futility criteria before Amendment 2 were defined as follows: If 4 or fewer subjects among 30 subjects in Part 1 achieve RBC TI lasting at least 8 weeks, the study will be stopped unless there is compelling clinical evidence of efficacy in one or more other endpoints (eg, transfusion reduction, erythroid improvement). Upon review of the efficacy and safety data observed with the 7.5 mg/kg dose among 32 subjects in Part 1, a subset of 13 subjects was identified with higher hematologic response rates. These were subjects with non-del(5q) MDS and without prior exposure to either hypomethylating agents or lenalidomide. As of Amendment 2, Part 1 was expanded to include only subjects who meet these criteria, with the goal to confirm the safety and efficacy data seen in this subset and to re-confirm the dose. Twenty-five additional subjects with non-del(5q) MDS and without prior exposure to either hypomethylating agents or lenalidomide,

so called target population, were enrolled for a total of 38 (from 57 enrolled in Part 1) that met these criteria.

Since data from Part 1 for this target population show clinical benefit of treatment with imetelstat (see Section 3.2 for a summary of data from the 38 subjects in the target population), Part 2 of the study has been initiated in subjects with non-del(5q) MDS and without prior exposure to either hypomethylating agents or lenalidomide. Enrollment into the study was temporarily held between Part 1 and Part 2 while safety and efficacy data were analyzed.

Part 2 is a double-blind, randomized design to compare the efficacy of imetelstat with placebo. Approximately 170 eligible subjects (non-del(5q); no prior lenalidomide or hypomethylating agents) will be randomized in a 2:1 ratio to receive either imetelstat or placebo, respectively in the main study. Randomization will be stratified by prior RBC transfusion burden (≤ 6 or >6 units RBC) and by IPSS risk group (low risk versus intermediate-1 risk). Prior RBC transfusion burden is defined as the maximum number of RBC units transfused over an 8-week period during the 16 weeks prior to Randomization. In addition to the main study of Part 2, a Ventricular Repolarization substudy will enroll approximately 45 subjects to be randomized 2:1 to receive either imetelstat or placebo.

Each part of the study will consist of 3 phases: a Screening Phase of up to 28 days during which subject eligibility will be reviewed and approved by the sponsor prior to C1D1 (Part 1) or Randomization (Part 2); a Treatment Phase that will extend from C1D1 (Part 1) or C1D1 (Part 2) until disease progression (PD), or unacceptable toxicity, or withdrawal of consent; and a Posttreatment Follow-up Phase which will continue until death, lost to follow-up, withdrawal of consent, or the end of the study (whichever occurs first). The end of the main study is defined as 24 months after the randomization of the last subject in the main study of Part 2. The end of the study is defined as after all subjects have completed participation in the Extension Phase (at least 5 years from the first dose of imetelstat in Part 2 of the main study, or 3 years of post-treatment follow-up from the last dose of study treatment, whichever occurs later, or until death, withdrawal of consent, study termination, or until a subject is lost to follow-up).

Subjects enrolled in Part 1 will continue through the Part 1 treatment and posttreatment follow-up phases after initiation of Part 2. Subjects enrolled in Part 1 of the study are not eligible to enroll in Part 2.

For Part 2, an additional 45 evaluable subjects will be enrolled in a separate substudy investigating the effects of imetelstat exposure on ventricular repolarization. Details regarding the Ventricular Repolarization substudy, including eligibility criteria and study procedures (including Time and Events Table) for participating subjects are provided in Attachment 11.

The term 'Study Drug', as used in this protocol, refers to either imetelstat or placebo in Part 2. Each treatment cycle will consist of 4 weeks (28 days). All subjects receiving study drug must be premedicated to prevent infusion reactions (see Section 6.2). The starting dose of the study drug is 7.5 mg/kg every 4 weeks. In Part 1 of the study, subjects whose dose was previously escalated (before Amendment 2) may continue at the 9.4 mg/kg dose. Study drug dose delay or reduction

for Grade 3 or Grade 4 toxicities will be instituted as per the instructions provided in Table 7, Table 8, Table 9, and Table 10.

Supportive care, including transfusions or myeloid growth factors, is to be administered to all subjects as needed per investigator discretion and according to local standard practices.

All study procedures will be conducted according to the Time and Event Schedules for Part 1 and Part 2 as per Table 1 and Table 3, respectively. Subjects who have enrolled into the Ventricular Repolarization substudy of Part 2 prior to Protocol Amendment 7 will continue the study assessments as required for the main study. Assessment of disease response and disease progression will be conducted based on the modified IWG Response Criteria 2006 for MDS (Modified IWG 2006),⁷ and robust transfusion data will be collected for all subjects (see Section 9.3.1.1 for details). For Part 2, in addition to local disease response evaluations, which may be used for treatment decisions, an Independent Central Pathology Reviewer will review bone marrow assessments performed at screening to confirm diagnosis and eligibility at the time of each bone marrow assessment throughout the duration of the main study. Following investigator-assessed CR, PR, or mCR, in subjects with >5% baseline bone marrow aspirate blasts, aspirate should be repeated 4 to 8 weeks later for confirmatory purposes, if clinically feasible. An Independent Review Committee (IRC) will be established to adjudicate investigator-assessed disease response (CR, PR, mCR, or cytogenetic response). Central laboratory results will also be used for assessment of the HI-E response. Safety evaluations will include adverse event monitoring, physical examinations, electrocardiogram (ECG) monitoring, clinical laboratory parameters (including hematology and chemistry), vital sign measurements, and Eastern Cooperative Oncology Group (ECOG) performance status.

The sponsor will review the safety data on an ongoing basis to ensure the safety of the subjects enrolled in this study. In addition, all hepatic adverse events and LFT abnormalities will be reviewed at least on a quarterly basis, and more frequently if needed, by an Independent Hepatic Expert Committee (HEC) (see Section 11.12). An Independent Data Monitoring Committee (DMC) will be established for the study to monitor safety data. The DMC will meet periodically to review safety data and after the review, the DMC will make recommendations regarding the conduct of the study. The details will be provided in a separate independent DMC charter. Refer to Section 11.11, Independent Data Monitoring Committee, for additional details.

[figure not shown]
Subjects benefiting from imetelstat treatment at the end of the main study (ie, 24 months after last subject randomized in the main study of Part 2) per investigator assessment may continue to receive imetelstat during the Extension Phase. All subjects in the Posttreatment Follow-up Phase of the main study will also continue in the Extension Phase for assessment of survival status, subsequent anticancer therapy, and monitoring of disease progression, including progression to AML (Table 5 and Figure 3). Subjects will be followed in the Extension Phase for at least 5 years from the first dose of imetelstat received in Part 2 of the main study (including treatment and follow-up), or 3 years of post-treatment follow-up from the last dose of study treatment, whichever occurs later, or until death, withdrawal of consent, study termination, or until a subject is lost to

follow-up. Subjects in the QTc substudy may also enter the Extension Phase after the clinical cut off for the primary analysis is reached for the substudy.

During the Extension Phase, the Independent HEC will be available to review all hepatic adverse events and liver function test abnormalities at least on a quarterly basis, or more frequently if needed.

With Protocol Amendment 8, Part 1 of the study will close as all subjects in Part 1 have already discontinued treatment and study will have already met the duration of follow-up defined for the Extension Phase (ie, at least 5 years from the first dose of imetelstat, or 3 years of post-treatment follow-up from the last dose of study treatment, whichever occurs later). Any subjects remaining in follow-up will be discontinued from the study. Therefore, the Extension Phase does not apply to Part 1 subjects.

[figure not shown]
The study endpoints are listed in Section 9.2.

Figure 2: Schematic Overview of the Study: Part 1 and Main Study of Part 2

a. Supportive care, including transfusions or myeloid growth factors, is to be administered as needed per investigator discretion and according to local standard practices.

b. Enrollment in Part 1 was expanded from up to 30 subjects to approximately 55 subjects in Amendment 2.

c. Beginning with Amendment 2, dose escalation to 9.4 mg/kg is no longer permitted for subjects enrolled in Part 1. Part 1 subjects whose dose was previously escalated (before Amendment 2) may continue at the 9.4 mg/kg dose.

Figure 3 Overview of the Extension Phase Following Amendment 8

*Subjects randomized to the placebo arm in the main study will enter the Extended Follow-up Phase part of the Extension Phase.

3.2. Study Design Rationale

Myelodysplastic syndromes are characterized by clonal myeloproliferation that arises from malignant progenitor cell clones that have shorter telomeres and multiple clonal genetic abnormalities. Telomerase is highly activated and continually upregulated in malignant progenitor

clones enabling continued and uncontrolled proliferation. While TA is generally undetectable in normal somatic cells, it is expressed in approximately 85% of human cancers as well as in cancer progenitor cells, which are believed to play a critical role in dysregulated cell growth and tumor metastasis.²⁰ In MDS, TA and expression of hTERT are significantly increased as compared to healthy controls.^{4,5} Myelodysplastic syndrome patients with high TA have been shown to have a significantly shorter OS as compared to those with lower TA.¹⁷ In addition, the average TL has been shown to be significantly shorter in MDS patients as compared to healthy controls^{30,40} and progression of the disease and conversion of MDS to AML are connected with progressive decrease in TL.⁴³ Several studies showed that higher TA and hTERT, and shorter TL correlate with IPSS risk score in MDS.^{5,38,52} In low risk MDS patients, short telomeres and high TA in addition to other factors were reported as poor prognostic features.^{37,51} Given the role of TA in preventing cell senescence and apoptotic cell death in immortalized cells such as tumor cells,²⁴ inhibition of TA constitutes an attractive therapeutic approach in MDS.

Randomization and Treatment Groups

This is a multicenter, 2-part, study to compare the efficacy of imetelstat to placebo in transfusion-dependent subjects who have MDS that is relapsed/refractory to ESA treatment.

Part 1 of the study was an open-label single-arm design. Randomization will be used in Part 2 of the study to minimize bias in the assignment of subjects to treatment groups, to increase the likelihood that known and unknown subject attributes (eg, demographic and baseline characteristics) are evenly balanced across treatment groups, and to enhance the validity of statistical comparisons across treatment groups. The 2:1 randomization scheme has been chosen to limit the number of subjects in the placebo group, to increase the likelihood of subjects receiving active treatment of imetelstat for low or intermediate-1 risk MDS, and to study safety of imetelstat in a larger cohort.

Subjects will be stratified in the randomization process according to prior RBC transfusion burden (≤ 6 or >6 units RBC) and by IPSS risk group (low versus intermediate-1) to ensure equal distribution across treatment groups. Prior RBC transfusion burden is defined as the maximum number of RBC units transfused over an 8-week period during the 16 weeks prior to C1D1 (Part 1) or Randomization (Part 2).

Blinded treatment will be used to minimize the potential influence of treatment assignment knowledge on clinical decision making, such as transfusion administration, and to reduce potential bias during data collection and evaluation of clinical endpoints; thus, ensuring the robustness and integrity of the study. The primary objective and secondary efficacy objectives of Part 2 of the main study are to compare RBC TI, time to RBC TI, and duration of RBC TI between the 2 treatment groups (imetelstat and placebo). The use of the modified IWG 2006 criteria to assess disease progression is intended to promote uniformity across study centers. It is the intent that all subjects, investigators, and study team members, except some required project roles (eg, members associated with DMC and HEC), will remain blinded to treatment group assignment at least until the primary efficacy analysis (12 months after the last subject is randomized in the main study of Part 2). As of Protocol Amendment 8, subjects, investigators, and study team members will be

unblinded after primary efficacy analysis. Upon unblinding the subjects after the primary analysis, subjects on imetelstat may continue treatment per investigator discretion. Subjects on placebo may discontinue treatment and enter the posttreatment follow-up phase of the study. The investigator will discuss treatment options with subject's discontinuing study treatment and record treatment selection as part of subsequent therapy.

Study Population

Limited treatment options are available for patients who are RBC transfusion dependent, who have IPSS low risk or intermediate-1 risk MDS that is relapsed/refractory to ESA treatment whether because they have already received at least one prior treatment with an ESA without achieving or maintaining a response or have high levels of endogenous erythropoietin and are considered unlikely to respond. The median survival for low-risk MDS patients for whom ESA treatment has failed is about 3.5 years, which is considerably shorter than predicted at the time of diagnosis. Therefore, there remains a highly unmet need for effective treatments for these patients.

Review of the data of Part 1 (Section 1.1.5) support further evaluation of imetelstat in subjects that are non-del(5q) and have not been previously treated with either a hypomethylating agent or lenalidomide, hence this represents the target population of Part 2 of the main study.

Endpoints

The primary endpoint of this main study is the proportion of subjects who achieve 8-week RBC TI, defined as absence of RBC transfusion during any consecutive 8-week period. Transfusion independence for 8 weeks is a clinically meaningful and robust endpoint which is included in the modified IWG 2006 response criteria and has been the basis for regulatory approvals.

The rate of hematologic improvement-erythroid (HI-E) will provide further explanation of the hematologic response (as per modified IWG 2006 response criteria). The time to progression to AML and OS are important endpoints considering that the natural history of MDS includes transformation to AML in a proportion of patients.

The depth of the response will be captured by assessment of CR, PR, and mCR per modified IWG 2006 response criteria. The data from Study CP14B019 suggest the potential for disease modification and long-term benefit to patients. Duration of responses will be assessed. Subjects will be followed for OS.

Pharmacokinetic and Immunogenicity Evaluations

Pharmacokinetics of imetelstat have not been characterized in MDS patients. Intensive pharmacokinetic sampling analysis was performed in up to approximately 15 subjects in Part 1 and will be performed in up to approximately 30 subjects (active treatment) in the Ventricular Repolarization substudy (Part 2). Along with sparse pharmacokinetic sampling in the remainder of subjects, this will allow for estimation of individual pharmacokinetic parameters and build a population pharmacokinetic model. The specific time points for measurement of imetelstat plasma concentrations are chosen to gather information about the pharmacokinetic properties of imetelstat. Anti-drug antibodies will be assessed during the study.

Biomarkers

Based on the mechanism of action of imetelstat and results from preclinical and previous clinical studies, imetelstat is expected to cause TA inhibition, TL shortening and hTERT level reduction. Blood samples will be collected from all subjects to evaluate TA, TL, or hTERT RNA level changes as pharmacodynamic biomarkers. Karyotyping on bone marrow samples from all subjects in the main study (imetelstat and placebo) will be performed to evaluate cytogenetic response by assessing the reduction or depletion of clones with cytogenetic abnormalities. Blood and bone marrow samples from all subjects in the main study will be analyzed to characterize mutation status and mutation change, immunophenotyping, and perform RNA seq for evaluation of potential inter-individual variability in clinical outcomes or identification of population subgroups that respond differently to imetelstat.

Patient-Reported Outcomes

The Functional Assessment of Cancer Therapy – Anemia (FACT-An), is included in order to provide an assessment of the subject’s functional status, well-being, and symptoms over time. The Quality of Life in Myelodysplasia Scale (QUALMS)¹ is a new MDS-specific health-related quality-of-life measure, and the Patient Global Impression of Change (PGIC) captures the patient’s perspective of improvement or decline in MDS over time. The EuroQol-EQ-5D-5L (EQ-5D-5L) assessment is included to provide estimates of utility to include in future cost effectiveness models.

Imetelstat Dose and Regimen Selection

In Study CP14B019, subjects with MDS received a starting imetelstat dose of 7.5 mg/kg every 4 weeks. Subsequent doses were adjusted based on investigator assessment of toxicity and clinical response, resulting in individualized regimens that included 6.0 mg/kg, 7.5 mg/kg and 9.4 mg/kg every 4 weeks. In addition, neither prolonged thrombocytopenia nor neutropenia were observed in the MDS cohort. Based on the available data, a starting dose regimen of 7.5 mg/kg every 4 weeks demonstrated an acceptable safety profile and favorable efficacy that warrants further clinical investigation. Efficacy and safety data from Part 1 of the current study support the use of this dosing regimen in Part 2 of the study.

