The distributions of OS, PFS, and time to progression to AML will be compared using a stratified log rank test for the ITT population. The Kaplan-Meier method will be used to estimate the distribution for each treatment. The treatment effect (hazard ratio) and its 2-sided 95% confidence intervals are to be estimated using a stratified Cox regression model with treatment as the sole explanatory variable. The reasons of censoring in time to progression to AML will be tabulated.

The time to 8-week and 24-week RBC TI will be summarized descriptively based on ITT 8-week and 24-week RBC TI responders, respectively. The Kaplan-Meier method will be used to estimate the distribution of duration of RBC TI based on ITT 8-week and 24-week RBC TI responders, respectively.

The amount and relative change in RBC transfusions will be summarized descriptively by treatment by time point.

Change from baseline in scores from QUALMS, FACT-An, and EQ-5D-5L will be summarized descriptively by treatment group. The PRO measure of interest and analysis methods (eg, responder analysis, longitudinal analysis with repeated measures) will be specified in the Statistical Analysis Plan.

A sequential gate-keeping procedure will be implemented to ensure that the overall type I error rate for the secondary endpoints is controlled. Details of selected secondary endpoints to be tested

and the testing procedure will be specified in the Statistical Analysis Plan.

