3.2.2 Secondary Endpoints

- Safety of imetelstat in subjects with MDS (eg, incidence, intensity, and type of adverse events, vital signs measurements, clinical laboratory values, ECGs changes, and deaths);
- 24-week RBC TI rate, defined as the proportion of subjects without any RBC transfusion during any consecutive 24 weeks (168 days) starting from Study Day 1;
- Time to the 8-week (24-week) RBC TI, defined as the interval from Study Day 1 to the first day of the first 8-week (24-week) RBC TI period;
- Duration of RBC TI, defined as the first day of the longest RBC TI period to the date of the first RBC transfusion after the TI period starts;
- Rate of hematologic improvement, including hematologic improvement-erythroid (HI-E), per modified International Working Group (IWG) 2006;
- Rates of CR, PR, or mCR per modified IWG 2006;
- OS, defined as the interval from Study Day 1 to death from any cause. Survival time of living subjects will be censored on the last date a subject is known to be alive or lost to follow-up;
- Progression free survival, defined as the time interval from Study Day 1 to the first date of disease progression or death from any cause, whichever occurs first.
- Time to progression to AML, defined as the interval from Study Day 1 to the date of AML diagnosis.
- Amount and relative change in RBC transfusions;

- Rate of myeloid growth factors usage, defined as the proportion of subjects receive any myeloid growth factors starting from Study Day 1; duration of myeloid growth factor administered starting from Study Day 1;
- Pharmacokinetic parameters (eg, C_{max} , AUC_{0-t}), and immunogenicity of imetelstat (eg, antibodies to imetelstat);
- Medical resource utilization data including hospitalization, emergency room visits, and hematology specialist visits (Part 2 only);
- ECG parameters including change in QT interval by Fridericia's correction method ($\Delta QTcF$) in the Ventricular Repolarization substudy (Part 2 only).

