4.5.1 Efficacy Analysis Sets

Part 1 (Phase 2):

All Treated analysis set: includes all subjects who receive at least one dose of study drug. This analysis set will be used for all analyses of efficacy endpoints (except time to the 8 or 24-week RBC TI and duration of RBC TI), analyses of disposition, demographics, and baseline disease characteristics.

All Treated 8-week (24-week) TI responder analysis set: includes all treated subjects who do not have any RBC transfusion during any consecutive 8 (24) weeks starting from Study Day 1 until subsequent anti-cancer therapy if any, with the TI starting date between Study Day 1 and date of last dose of study medication + 30 days or End of Treatment Visit whichever occurs first. This analysis set will be used for analyses for time to RBC TI and duration of RBC TI.

Part 2 (Phase 3):

Intent-to-Treat (ITT) analysis set: includes all subjects randomized into the main study. This analysis set will be used for all analyses of efficacy and patient-reported outcomes (PRO) endpoints (except time to the 8 or 24-week RBC TI and duration of RBC TI), analyses of disposition, demographic, and baseline disease characteristics. Subjects will be classified according to assigned treatment group, regardless of the actual treatment received.

ITT 8-week (24-week) TI responder analysis set: includes all subjects in the ITT analysis set who do not have any RBC transfusion during any consecutive 8 (24) weeks starting from Study Day 1 until subsequent anti-cancer therapy if any, with the TI starting date between Study Day 1 and date of last dose of study medication + 30 days or End of Treatment Visit whichever occurs first. This analysis set will be used for analyses for time to the RBC TI and duration of RBC TI.

Modified ITT (MITT) analysis set: includes all ITT subjects who received at least one dose of study drug according to assigned treatment group. This analysis set will be used for sensitivity analyses for 8-week and 24-week RBC TI in the case there are subjects who were dosed, but didn't receive the assigned treatment.

Per-protocol (PP) analysis set: This analysis set is a subset of the ITT analysis set. Subjects with key protocol deviations will be excluded from the PP analysis set. The categories and terms of the key protocol deviations leading to exclusion are defined in the project-specific Protocol Deviation Specification.

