4.9.3.2 Analysis Methods

Part 1 (Phase 2):

The proportion of subjects with 24-week RBC TI, CR, PR, and hematologic improvement, and other binary endpoints, will be summarized with percentage along with its 95% 2-sided exact Clopper-Pearson CI. The time to 8-week RBC TI and time to 24-week RBC TI will be summarized descriptively based on 8-week and 24-week TI responder analysis set, respectively. The Kaplan-Meier method will be used to estimate the distribution of duration of RBC TI based on 8-week and 24-week TI responder analysis set, respectively. The distribution of OS, PFS, and time to progression to AML will be summarized using similar Kaplan-Meier methods.

Part 2 (Phase 3):

The 24-week RBC TI rates will be summarized with frequencies and percentages along with 2-sided 95% exact Clopper-Pearson CIs for the 2 treatment groups. Difference in TI and its 95% CI will be presented using Wilson Score method [1]. The comparison will be based on a stratified CMH test adjusting for the stratification factors at a two-sided significant level of 0.05.

Sensitivity analyses will be performed for Part 2 to evaluate the robustness of the 24-week RBC TI endpoint and includes:

- CMH test of 24-week RBC TI based on MITT analysis set in the case there are subjects who were dosed, but didn't receive any assigned treatment;
- CMH test of 24-week RBC TI based on per-protocol analysis set;

The time to 8-week and 24-week RBC TI will be summarized descriptively for the 2 treatment groups based on ITT 8-week and 24-week TI responder analysis set, respectively. The Kaplan-Meier method will be used to estimate the distribution of duration of RBC TI based on ITT 8-week and 24-week TI responder analysis set, respectively, and will be compared between two treatment groups using stratified log rank test based on ITT 8-week responder analysis set. The distribution of cumulative duration of RBC TI ≥ 8 weeks (sum of all durations of RBC TI ≥ 8 weeks) will be estimated by Kaplan-Meier based on ITT 8-week responder analysis set as well.

The proportion of subjects with hematologic improvement, CR, PR, or mCR per modified IWG 2006, and other binary endpoints will be evaluated using the same statistical methods as for the endpoint of 24-week RBC TI rates. The 8-week RBC TI rate in the first 24 weeks and 48 weeks (proportion of subjects who had RBC TI ≥ 8 weeks in the first 24/48 weeks) will be evaluated similarly.

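### Time to RBC TI is named in Protocol 3.2 as a between-arm comparison but is only described among responders, a post-randomisation subset that cannot support one

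*Protocol*

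**What the plan says.** Protocol 3.2 (Study Design Rationale, in the part on randomisation and treatment groups) states that the primary and secondary efficacy objectives of Part 2 "are to compare RBC TI, time to RBC TI, and duration of RBC TI between the 2 treatment groups (imetelstat and placebo". The formal secondary objective in Protocol 2.1 is weaker: "To assess the time to RBC TI and duration of RBC TI". SAP 2.2 repeats that weaker form.

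The endpoint is "defined as the interval from Study Day 1 to the first day of the first 8-week (24-week) RBC TI period" (SAP 3.2.2; Protocol 9.2.2 agrees). Neither definition says what value a subject takes who never reaches TI.

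On analysis, Protocol 11.4 says "The time to 8-week and 24-week RBC TI will be summarized descriptively based on ITT 8-week and 24-week RBC TI responders, respectively". SAP 4.9.3.2 says the same by arm: "RBC TI will be summarized descriptively for the 2 treatment groups based on ITT 8-week and 24-week TI responder analysis set". SAP 4.5.1 assigns efficacy endpoints to the ITT set "except time to the 8 or 24-week RBC TI and duration of RBC TI".

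The other two quantities named in Protocol 3.2 do get a between-arm analysis. RBC TI is tested by stratified CMH in the ITT set. Duration of TI gets a stratified log-rank test in SAP 4.9.3.2, though among 8-week responders only. Time to TI is not in the tested family (SAP 4.9.1.3).

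SAP 4.9.3.2 also plans the proportion of subjects with an 8-week TI in the first 24 and first 48 weeks, evaluated like the other binary endpoints. By the SAP's own rules that means the ITT set, a stratified CMH test and a difference with a Wilson-score interval.

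**The concern.** Of the three quantities that Protocol 3.2 sets out to compare, time to TI alone has no between-arm analysis under its own name. The summary that carries the name conditions on response. Response is an outcome of treatment, so imetelstat responders and placebo responders are not groups formed by randomisation.

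Two medians printed side by side will nevertheless be read as a comparison. If TI without active treatment tends to start earlier than drug-induced TI, the imetelstat median is pulled later by the extra responders that the drug produces. The table could then suggest slower onset on imetelstat while more imetelstat subjects are in TI at every time. At stake is the interpretation of one secondary endpoint, not the primary conclusion.

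**Working it through.** **1. The planning rates.** The plan gives no figure for time to TI, so the responder counts rest on the sample-size section (Protocol 11.3, SAP 4.12): 30% vs 7.5%, 2:1, continuity-corrected chi-square, two-sided 0.05, 150 subjects, about 88% power. With 100 and 50 subjects, the continuity-corrected formula gives 87.6% and exact enumeration gives 88.7%. Dropout: 150 / 0.90 = 167, rounded to about 170 (115 + 55). The plan's figures reproduce.

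**2. Size of the responder sets.**
- Imetelstat: 115 × 0.30 = 34.5, so about 70% of the arm is left out.
- Placebo: 55 × 0.075 = 4.1, so about 92% of the arm is left out.
- With X ~ Binomial(55, 0.075): P(X ≤ 2) = 21% and P(X = 0) = 1.4%.

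**3. Can the responder-only medians point the other way?** The documents give one onset figure: the Part 1 imetelstat target population had a median of 8.1 weeks, range 0.1 to 33.1 (Protocol 1.1.5). They give none for placebo. Assumptions:
- Every subject in both arms keeps a 7.5% chance of TI without drug effect, with median onset m weeks.
- A further 22.5% of imetelstat subjects respond to drug, with median onset 8.1 weeks.
- Onsets are lognormal with log-scale SD 0.8.

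With F(t; m) the lognormal distribution function, the proportion that has started TI by week t is:
- placebo: 0.075 × F(t; m)
- imetelstat: 0.075 × F(t; m) + 0.225 × F(t; 8.1)

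The imetelstat proportion is the placebo proportion plus a positive term, so it is larger at every t. For m = 4:

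| Week | Imetelstat | Placebo |
|---|---|---|
| 4 | 8.0% | 3.7% |
| 8 | 17.2% | 6.1% |
| 24 | 27.9% | 7.4% |

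The responder-only median is nevertheless 6.9 weeks on imetelstat and 4.0 on placebo. Simulating trials of 115 and 55 subjects (those without a placebo responder set aside), the observed imetelstat median is the later one in these shares:

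| Assumed placebo-type median onset (weeks) | Trials in which placebo looks faster |
|---|---|
| 2 | 97% |
| 4 | 84% |
| 8.1 (same as drug-induced) | 48% |
| 12 | 26% |

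The 8.1 weeks is an overall Part 1 median used here for drug-induced onset. With m = 4 and a drug-induced median of 10 weeks, the overall imetelstat median becomes 8.1 and the share is 90%.

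**4. What the planned landmark rates cover.** They use the ITT set and compare arms, but for 8-week TI only, at Weeks 24 and 48 only, and they count a TI period achieved within the window rather than started. Half of the Part 1 responders had started by 8.1 weeks, so much of the onset pattern lies before the first landmark.

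**The case against.** Four points on the other side deserve weight.

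- *The objective is only to assess.* Protocol 2.1 and SAP 2.2 say so, and a descriptive summary can satisfy that. The comparative verb stands only in a rationale paragraph about blinding. This stands: a reader might infer that a formal objective goes unanswered, and the documents do not support that. What remains is that 3.2 and 2.1 disagree.
- *Timing in randomised subjects is already compared.* A reader might infer that nothing in the plan compares how soon subjects reach TI. The 24- and 48-week ITT rates contradict that for 8-week TI. They leave the gaps listed in step 4 and are not presented as the time-to-TI analysis.
- *The reversal rests on a premise about placebo.* It is tempting to say that placebo responses are chance transfusion-free periods starting near Day 1 while drug responses build slowly. No passage says so, and Part 1 imetelstat onsets themselves began at 0.1 weeks. Hence the range: with equal onset medians the direction is close to a coin toss.
- *Few placebo responders are a reason to keep the summary descriptive.* Agreed. It would be wrong to fault the plan for lacking a usable confidence interval for the placebo median, because it proposes none.

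It can also be said that cumulative incidence mixes response rate with speed, and that onset among responders is a fair descriptive question. That supports keeping the responder summary, but not reading it across arms.

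**Conclusion.** The inconsistency is real and modest. Protocol 3.2 promises a between-arm comparison of time to TI. Protocol 11.4 and SAP 4.5.1 and 4.9.3.2 provide a responder-only description, on about 34.5 vs 4.1 expected subjects, which cannot serve as that comparison. Timing is partly covered by the ITT rates in the first 24 and 48 weeks. There is no time-to-TI curve, no view before Week 24 and no counterpart for 24-week TI.

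A misleading direction is possible, not established. It ranges from about 97% to 26% of trials as the assumed placebo-type median goes from 2 to 12 weeks, given the planning rates, a drug-induced median of 8.1 weeks and lognormal onset with log-scale SD 0.8. A reader should not conclude that the summary will favour placebo, nor that the primary result is affected: the primary test, alpha and sample size stand as they are.

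**What to change.** In SAP 4.9.3.2, add for the ITT set, by arm, the cumulative incidence (Aalen-Johansen) of starting the first 8-week TI period, and likewise the first 24-week period.
- Competing events: death, subsequent anti-cancer therapy, and closing of the TI start window as the SAP defines it (last dose + 30 days or the End of Treatment visit, whichever is first; Study Day 31 if never treated).
- Censoring: subjects still in the window at data cut-off minus 56 days (168 days for 24-week TI).
- Report between-arm differences with 95% CI at fixed weeks, for example 8, 24 and 48, outside the alpha chain.
- State how these relate to the planned 24- and 48-week rates, which count TI achieved rather than started.

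Keep the responder-only summary, labelled descriptive and non-comparative. Reconcile the comparative verb in Protocol 3.2 with *assess* in Protocol 2.1. If the sponsor does not want the added analysis, the minimum is to reword 3.2 and label the responder summary.

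Cost: one table and one figure, from dates already collected or derived. No new data, no alpha, and no change to the primary analysis or sample size.
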